24 male and female outpatients aged 4-17 with a primary diagnosis of Autism Spectrum Disorder.

-Note on sample size: The sample size is low due to this being a pilot feasibility study and the primary aim of the study is not to examine the effectiveness of oral glutathione as a treatment but rather examine the functionality of providing oral glutathione on the blood level, the data will likely be used for future studies on treatment or grant applications. There also is no external sponsor, therefore internal funding limits the number of subjects.

Participant Exclusion:

For this study, children under the age of 4 and adults over the age of 17 will be excluded. The rationale for this is that the study population of interest are pediatric subjects in the children and adolescent age ranges.

Data Analysis:

Primary analyses will be intent-to-treat with last observation carried forward. Changes in the blood level of glutathione will be the primary outcome measure. For both primary and secondary measures, random regression analysis will be conducted using the MIXREG program

Demographic and baseline visit characteristics of the Glutathione treatment patients will be documented. Primary and secondary measures will be examined using analysis of variance modeling analyses (SPSS). The difference in the overall level of posttreatment values, the main effect for treatment, will be the test of primary interest. Analyses will be performed on all available data by the use of an intention-to-treat population (last observation carried forward). All patients who return for at least 1 follow-up visit will be included in the intention-to-treat population. Effect sizes will also calculated using the Cohen effect size index d. A d of 0.2 is considered a small effect size, 0.5 is medium, and 0.8 is large. Partial eta squared (η 2), which is the proportion of the effect + error variance that is attributable to the effect, will be calculated. Interpretation of η 2 is that greater than 0.2 is a large effect size, greater than 0.1 is a medium effect size, and greater than 0.05 is a small effect size.

The CGI severity scale will be used to assess clinically significant change after treatment. For someone to have a clinically significant change, her or his final CGI severity score had to be less than the cutoff score, and her or his change from baseline had to be greater than the reliable change index

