Unanticipated (unexpected) problems/events, those that are not already described as potential risks in the consent form, or not part of an underlying disease, will be reported to the IRB within 10 business days. The same will be done for serious problems/events and, in the opinion of the investigator, are possibly, probably or definitely related to the research procedures. A follow-up report will also be submitted to the IRB with any documentation related to a previously submitted adverse event.

Procedure:

Twenty-four (24) subjects will be recruited to receive oral Glutathione reduced in this open-label trial. All parents of the subjects will be provided with informed consent forms and verbal assent from subjects ≥ 6 years of age will be obtained after an age appropriate version of the informed consent forms are read to them. The Child Psychiatry clinicians/nurses, patients and parents will be aware of the medication name and dosing schedules as indicated. The clinic nurse will obtain vitals at each visit. Glutathione will be the only study medication dispensed to subjects for this study. Subjects will be told to take the first dose of study medication after breakfast each day and the second dose in the evening after dinner. Subjects will be told to monitor and report any side effects experienced to the study staff at each visit or immediately if they wish (via one of the

Page 12 of 17 IRB19-0017 Version 2: date: 4/11/19 multiple telephone numbers for the study physicians and study staff given to them at each visit).

Psychotherapy of any form (including cognitive-behavioral therapy) will be reported to the PI during the study.

Subjects will be evaluated with the Aberrant Behavior Checklist (ABC), Social Responsiveness Scale (SRS) and CGI at screening and at each visit for the remainder of the study. Medication side effects will be evaluated at each study visit. A tablet count will be kept for each dose of medication taken to monitor adherence.

Dosing Regimen for Glutathione

The proposed dose range for Glutathione in this study will be 1000mg-3000mg/day based on the subject's weight. A previous observational study of children with Cystic Fibrosis showed that this population responded well and were able to absorb Glutathione with a daily dose of 65mg/kg (10).

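### Size words are attached to uncorrected effect sizes with no confidence interval; at n = 24 a measure with no true change passes the *small* partial eta squared line in about 3 of 10 analyses, counting both directions.

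*Combined protocol and SAP*

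**What the plan says.** The trial has one arm: "Twenty-four (24) subjects will be recruited to receive oral Glutathione reduced in this open-label trial" (Procedure). Glutathione is measured twice, at the initial visit and at study completion. The ABC, SRS and CGI are completed at every visit (Assessments, New Data Collection).

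The Data Analysis section names an analysis of variance and a random regression for the primary and secondary measures. It then names the test: "The difference in the overall level of posttreatment values, the main effect for treatment, will be the test of primary interest". It adds that two effect sizes will be calculated:

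- Cohen's d: "A d of 0.2 is considered a small effect size, 0.5 is medium, and 0.8 is large". The SD that standardises d is not named.
- Partial eta squared, "which is the proportion of the effect + error variance that is attributable to the effect". The cut-offs are "greater than 0.2 is a large effect size", then "greater than 0.1 is a medium effect size, and greater than 0.05 is a small effect size".

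The documents plan no confidence interval for any measure, no small-sample correction of either index, and no significance level. They do not link the size words to the result of the test. The note on sample size gives pilot status and internal funding as the reasons for 24 subjects, and says that "the data will likely be used for future studies on treatment or grant applications".

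**The concern.** Partial eta squared cannot be negative, so sampling error alone makes it positive. In a small one-arm study its average under no change lies close to the plan's *small* line. A word such as *small* or *medium* then says little about whether anything changed, and without an interval the reader cannot see how little. Partial eta squared also has no sign, whereas Aim 1 asks specifically whether glutathione increases.

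The trial has no power or precision calculation, and its data are expected to inform later work. Effect sizes are a natural input to such planning. If they are carried forward as words and point estimates, their uncertainty is lost.

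**Working it through.** The plan gives no power, precision or error figure for these labels, so there is nothing of its own to reproduce.

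**Inputs.** From the documents: n = 24, one arm; cut-offs 0.05, 0.1 and 0.2 for partial eta squared and 0.2, 0.5 and 0.8 for d; two time points for glutathione and repeated visits for the scales. Assumed: roughly normal changes, all 24 analysed, and the treatment main effect read as the within-child time effect, since there is no comparison group.

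**Step 1. Partial eta squared under no change.** With k time points, df1 = k − 1 and df2 = 23(k − 1). Partial eta squared then follows Beta(df1/2, df2/2) under sphericity. Its mean is df1/(df1 + df2) = 1/24 = 0.042 for any k, against a *small* line of 0.05.

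| Time points | P(> 0.05) | P(> 0.1) | P(> 0.2) |
|---|---|---|---|
| 2 (df 1, 23) | 28.3% | 12.4% | 2.5% |
| 5 (df 4, 92) | 31.2% | 4.4% | 0.04% |
| 7 (df 6, 138) | 30.5% | 2.2% | about 0 |

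The pre/post figures count rises and falls together. One direction alone is half: 28.3%/2 = 14.1% for *small* or more. If sphericity is replaced by AR(1) correlation of 0.5 to 0.8 with 5 to 7 time points (simulation), P(> 0.05) is 28.7% to 30.3%.

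**Step 2. What the lines mean at n = 24, pre/post.** With η² for partial eta squared, t = √(23η²/(1 − η²)) and d = t/√24 on the SD of change. Intervals come from inverting the noncentral t.

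| η² | t | two-sided p | d (95% CI) |
|---|---|---|---|
| 0.05 | 1.10 | 0.28 | 0.22 (−0.18 to 0.63) |
| 0.10 | 1.60 | 0.12 | 0.33 (−0.09 to 0.73) |
| 0.20 | 2.40 | 0.025 | 0.49 (0.06 to 0.91) |

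**Step 3. Cohen's d under no change.** On the SD of change, |d| ≥ 0.2 means |t| ≥ 0.2√24 = 0.980 on 23 df, which has probability 33.7%. On the baseline SD the rate depends on the pre/post correlation, which the documents do not give. By simulation it is 41.7% at 0.3, 33.8% at 0.5, 21.9% at 0.7 and 13.4% at 0.8.

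On the SD of change, the 95% CI is −0.21 to 0.60 around an observed d of 0.2, 0.07 to 0.92 around 0.5, and 0.33 to 1.25 around 0.8.

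**Step 4. What a correction does.** For pre/post, epsilon squared = 1 − (1 − η²)(24/23). An η² of 0.05 becomes 1 − 0.95 × 24/23 = 0.009. Applying the 0.05 line to the corrected value requires η² > 1 − 0.95 × 23/24 = 0.0896, and the rate under no change falls from 28.3% to 14.6%. Correction helps but does not replace an interval. For d, Hedges' factor at 23 df is 0.967, so 0.50 becomes 0.48, a minor change.

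**The case against.** The strongest reply is that the cut-offs are benchmarks beside a test, not a decision rule. The section names a test of primary interest, plans a random regression, and presents effect sizes as an addition. A reader would see the test result next to the label, and the sign of d would show a fall in glutathione. This stands in part. It rules out the claim that the label alone decides how a result is read. It does not supply an interval, and nothing in the plan stops a result with p = 0.28 from being described as a small effect, or one with p = 0.12 as a medium effect.

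Four stronger readings are tempting, and the documents do not support them:

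- *Three in ten null measures will look beneficial.* The rate counts both directions. In the favourable direction it is about 14% pre/post.
- *Noise is readily called medium on every measure.* That is mainly a two-time-point result, at 12%. For scales analysed over five visits it is about 4%.
- *The effect size is what later studies will use.* The sample-size note speaks of the data generally, and says that effectiveness is not the primary aim.
- *Attrition makes the problem worse.* It would: pre/post, 22 analysed gives 30.5% and 18 gives 35.7%. But these counts are assumptions. No dropout rate is stated, and the study is to end once 24 have completed.

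**Conclusion.** The point holds as a weakness in planned interpretation and reporting. The data and the planned test are not affected. Followed as written, the partial eta squared rule gives a null measure at least a *small* label in 28% to 31% of analyses at n = 24, across two to seven time points and under the AR(1) patterns tried. The corresponding rate for d cannot be fixed, because the standardiser is not named: it is 34% on the SD of change and 13% to 42% on the baseline SD over the correlations assumed. The *large* line is rarely crossed by chance (2.5% pre/post).

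These figures assume roughly normal changes and 24 children analysed. Because the remedy costs almost nothing and the results are meant to inform later work, the change should be made.

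**What to change.** Replace the effect-size sentences in Data Analysis with the following:

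- For each measure, report the mean change in its own units with a 95% CI.
- Report signed d with its standardiser named, Hedges' correction and a 95% CI (noncentral t where the SD of change is used).
- Report partial epsilon squared or omega squared in place of partial eta squared.
- Show the interval and the direction of change next to any size word.
- State that planning of later studies should take the whole interval into account.

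Two stricter rules may suggest themselves, and I advise against both. The first is to allow size words only when the interval excludes zero. At n = 24 pre/post that requires |d| > 2.069/√24 = 0.42, or partial eta squared above 0.157, so the *small* band could never be awarded. It would also select inflated estimates: in simulation with a true d of 0.2, the labelled values average about 0.53. The second is to plan later studies on the lower confidence limit. An observed d of 0.2 gives −0.21, which is unusable, and 0.5 gives 0.07, which is impractically small.

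The cost is a few lines of wording and slightly more reporting, with no new data. Some effects will look less favourable.

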Glutathione is a vital antioxidant agent, necessary for neutralizing reactive oxygen species (i.e. free radicals) and it is needed for optimal detoxification or removal of toxic substances from the human body (5, 7). There is evidence that indicates that children with Autism Spectrum Disorder have lower levels of plasma reduced Glutathione than in typically developing children (5). This finding has been observed across several neuropsychiatric conditions. The lower levels of glutathione that are seen in this population appear to be due to abnormalities found in the transsulfuration pathway, a pathway that is key for Glutathione production (5). The decreased or diminished levels of Glutathione can potentially lead to accumulations of reactive oxidative species which may cause functional changes in DNA, RNA, protein, lipid and carbohydrate systems, leading to cellular dysfunction (4). This redox variance appears to be involved in the pathogenesis of ASD and has been proposed by other studies (4).

According to the Centers for Disease Control, the prevalence of Autism Spectrum Disorder in 2014 was about 1 in 59 children (aged 8) in 11 communities across the US and has been increasing (2). The disorder occurs in all racial, ethnic and socioeconomic groups; and it is about 4 times more common among males than females (2). The concern over the last several years has been how to effectively treat patients with ASD and especially those with significant social impairments and behavioral dysregulation. Some children who have ASD can present with irritability, which refers to vocal and motoric outbursts demonstrating anger, frustrations and/or distress, often referred to "temper tantrums," "rages," or "meltdowns" (8). Along with irritability, some children may also present with problem behaviors, which refers to physical acts of aggression that have a high potential to result in harm to themselves, other people or property (8). The severity of the irritability or problem behaviors can have a significant impact on how the child is perceived

Page 4 of 17 IRB19-0017 Version 2; date: 4/11/19 by the outside world and can hinder their socialization with others even further. Other very important concerns are how the behaviors can jeopardize educational placements and can possibly lead to inpatient psychiatric admissions or long-term residential placements (8).

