		Visit					

Page 7 of 17 IRB19-0017 Version 2; date: 4/11/19

	Screening	1	2	3	4	5	6			
Consent Forms:	Х									
Medical Procedures on Child										
Blood draw		Х					Х			
Heart rate		х	Х	Х	Х	Х	Х			
Blood pressure		х	Х	Х	Х	Х	Х			
		Pare	nt Reports	on Child						
Aberrant Child Checklist	Х	Х	Х	Х	Х	Х	Х			
Social responsiveness Scale	Х	Х	Х	х	х	х	х			
Clinical Global Impression Scale	Х	Х	Х	Х	Х	Х	Х			
PRAS ASD	Х						Х			
Vineland-3	Х						Х			
Side effects checklist		Х	Х	Х	Х	Х	Х			

Subject Recruitment

All potential subjects for this study will be recruited through the Child and Adolescent Psychiatry Department Neurodevelopmental clinic and by Neuropsychological referral.

Subjects:

Inclusion criteria:

- 1) Boys and girls ages 4-17;
- 2) Current diagnosis of Autism Spectrum Disorder as determined by criteria in DSM-5
- 3) Parents of Children ages 4-17 with a current diagnosis of Autism Spectrum Disorder as determined by criteria in DSM-5

Exclusion criteria:

- 1) Unstable medical illness or clinically significant abnormalities on physical examination;
- 2) History of seizures;
- 3) History of Hematological disorders;
- 4) Myocardial infarction within 6 months;
- 5) Current pregnancy or lactation, or inadequate contraception in girls of childbearing potential;
- 6) Current or recent (past 3 months) DSM-5 substance abuse or dependence;
- 7) Illegal substance use within 2 weeks of study initiation;
- 8) Previous treatment with Glutathione;
- 9) Current treatment with N-acetylcysteine, milk thistle, Vitamin C, Vitamin B, Grape Seed Extract, Amino Acids, or Zinc (known to interfere with Glutathione level)
- 11) Current treatment with Dextromethorphan, D-cycloserine, Amantadine, Memantine, Lamotrigine or Riluzole (known to have glutamatergic properties)
- 12) Asthma (given this is rare, but possible worsening of asthma symptoms due to Glutathione)

Assessments:

Existing Data

Before beginning Glutathione, all subjects will have a psychiatric, medical, and family history evaluation completed as part of their standard clinical care.

New Data Collection

At the screening visit, all subjects will receive a physical examination. For all subjects, at the initial visit, blood work will be obtained for a baseline Glutathione level. Glutathione level will also be obtained at study completion. Total amount of blood to be obtained will be 4 teaspoons. PI will obtain neuropsychological evaluations report if it is available.

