The following instruments will be completed at each visit throughout the study: 1) Aberrant Behavior Checklist [ABC], a 58-item parent report subjective scale used for assessing problem behavior in subjects with intellectual and developmental disabilities; 2) Social Responsiveness Scale [SRS], a 65-item parent report questionnaire designed to use with children ages 4-17, providing age- and gender-referenced ranges and assessing social deficits pertaining to autism and

Page 9 of 17 IRB19-0017 Version 2; date: 4/11/19 other domains; and 3) the Clinical Global Impression scale [CGI]; 7 point scale to measure symptom severity. Also, readings of patients' heart rates and blood pressures will be obtained; and assessment of side effects will be done at each visit.

Note on ABC and SRS:

The ABC is a standardized scale used for assessing problem behaviors in subjects with developmental and intellectual disabilities. The items are divided into five subscales: 1) Irritability; 2) Lethargy/Social Withdrawal; 3) Stereotypic Behavior; 4) Hyperactivity; and 5) Inappropriate Speech. High scores are indicative of severe behavioral symptoms. The ABC will be used to track the subjects' problem behaviors and difficulties over the course of the study. The severity of the subjects' problem behaviors must be assessed and examined its relationship with a baseline blood level of glutathione. In addition, by using this scale, we can observe the overall effect of oral Glutathione on problem behaviors, especially comparing the end results to the baseline.

The SRS is being used for the same purpose, although it is being used for secondary outcome measures. It is a parent report questionnaire designed for use with children aged 4-17 and provides age- and gender-referenced, as well as raw scores for the following domains: total score (reflecting severity of social deficits pertaining to autism); receptive, expressive, cognitive and motivational aspects of social behavior; and autistic preoccupations. High scores are also indicative of severe behavioral symptoms.

Note on additional measures:

Clinical Global Impression (CGI) (Severity) scale will be used by the clinician to assess overall severity of problem behaviors in Autism Spectrum Disorder subjects at baseline. This will be used as a secondary outcome measure over the course of the study and relates to Aim #1.

Study Population/Sample Size

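### The CGI clinically-significant-change rule has no baseline condition: children starting near the scale minimum cannot qualify, and children starting below the cutoff can be credited without crossing it

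*Combined protocol and SAP*

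**What the plan says.** - **The rule (Data Analysis).** "For someone to have a clinically significant change, her or his final CGI severity score had to be less than the cutoff score", and in addition "her or his change from baseline had to be greater than the reliable change index". No value is given for the cutoff or the RCI, the direction of change is not stated, and nothing is required of the baseline score.
- **The analysis population (Data Analysis).** "All patients who return for at least 1 follow-up visit will be included in the intention-to-treat population". Baseline severity plays no part.
- **Entry (Inclusion criteria).** "Boys and girls ages 4-17" and "Current diagnosis of Autism Spectrum Disorder as determined by criteria in DSM-5". Neither the inclusion nor the exclusion list contains a minimum on the CGI, ABC or SRS.
- **What the CGI rates.** New Data Collection describes "the Clinical Global Impression scale [CGI]; 7 point scale to measure symptom severity". The Note on additional measures says that the clinician will use the severity scale "to assess overall severity of problem behaviors in Autism Spectrum Disorder subjects at baseline", and makes it a secondary outcome.
- **How common the target behaviours are (Background and Significance).** "Some children who have ASD can present with irritability". The same section says likewise of problem behaviours: some children, not all.
- **Timing (visit table).** The CGI is collected at screening, at Visit 1 and at every later visit.

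**The concern.** A cutoff shows a transition only for a child who started on the other side of it. An RCI threshold can be met only by a child with that much room to fall. The rule checks neither. A child rated very low at baseline is classed as having no clinically significant change even though no treatment could have produced one. A child already under the cutoff who falls further is classed as changed without having moved from one range to the other.

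If the classification is turned into a rate, no improvement and no room to improve are mixed together. With a single arm of 24 there is no control group sharing the same floor against which to read the figure. The sample size note expects the data to feed later treatment studies or grant applications, and there a rate that depends on baseline mix could mislead. Supplying the missing cutoff and RCI would not remove the problem, because the condition on the starting score would still be absent.

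**Working it through.** The plan has no figure of its own to reproduce. The check is what the stated rule allows on a bounded scale.

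**Inputs.** From the protocol: a 7-point scale, the two conditions, 24 children, and no baseline restriction. Assumed: scoring from 1 to 7 in whole points, change meaning a fall in score, and a whole-number cutoff of at least 2.

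**Step 1: who cannot qualify.** The largest possible fall from baseline b is b − 1. Qualifying needs a fall greater than the RCI, so it is impossible when b − 1 ≤ RCI.

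| RCI | Smallest qualifying fall | Baselines that cannot qualify |
|---|---|---|
| below 1 | 1 point | 1 |
| 1 to below 2 | 2 points | 1, 2 |
| 2 to below 3 | 3 points | 1, 2, 3 |

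These sets were the same for every cutoff tried (2, 3, 4 and 5).

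**Step 2: a plausible range for the RCI.** With RCI = 1.96 × √2 × SD × √(1 − r), where r is the reliability and both SD and r are assumed:

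| SD | r = 0.6 | r = 0.7 | r = 0.8 | r = 0.9 |
|---|---|---|---|---|
| 0.6 | 1.05 | 0.91 | 0.74 | 0.53 |
| 0.8 | 1.40 | 1.21 | 0.99 | 0.70 |
| 1.0 | 1.75 | 1.52 | 1.24 | 0.88 |
| 1.2 | 2.10 | 1.82 | 1.49 | 1.05 |

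Of the 16 values, 6 are below 1, 9 lie from 1 to below 2, and 1 is above 2. So the affected baselines could be 1 alone, 1–2, or 1–3, depending on inputs that the protocol does not give.

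**Step 3: who can be credited without crossing.** This needs a baseline below the cutoff and b − 1 > RCI. The highest baseline below the cutoff is cutoff − 1, so such children can exist when cutoff − 2 > RCI. Example: with cutoff 4 and RCI 1.5, a child going from 3 to 1 falls by 2 (more than 1.5) and ends below 4. The child is credited, having been below the cutoff from the start. With cutoff 3 this can happen only if the RCI is below 1.

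**Step 4: effect on a proportion, if one is reported.** If k of 24 analysed children cannot qualify, the ceiling is (24 − k)/24. The values of k are illustrative.

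| k | Ceiling | Reported rate if 40% (assumed) of the others qualify |
|---|---|---|
| 3 | 21/24 = 87.5% | 0.40 × 21/24 = 35.0% |
| 5 | 19/24 = 79.2% | 0.40 × 19/24 = 31.7% |
| 7 | 17/24 = 70.8% | 0.40 × 17/24 = 28.3% |
| 10 | 14/24 = 58.3% | 0.40 × 14/24 = 23.3% |

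Each such child lowers the ceiling by 1/24, about 4 percentage points. The credits in step 3 push the rate the other way and cannot be sized either.

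**The case against.** The strongest reply is that the harm depends on an analysis the plan never states. The rule classifies a person; no responder proportion, denominator or test is named. For a child with no room to improve, a label of no clinically significant change is also literally true. This stands as a limit: the effect on a rate follows only if the rule is applied across the stated intention-to-treat population.

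A reader might also infer that children with few or no problem behaviours will enrol. The documents support only that they may. Recruitment is through a neurodevelopmental clinic and neuropsychological referral, and DSM-5 criterion D requires clinically significant impairment. The protocol also describes the CGI in two ways. If it rates ASD symptoms generally rather than problem behaviours, baselines of 1 or 2 become less likely. Criterion D is still a condition of diagnosis, though, not a minimum CGI score, and the Note on additional measures ties the rating to problem behaviours.

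The size is wholly assumed: SD, reliability, the number of low starters and the 40% rate are not in the documents. If the RCI is below 1, only a baseline of 1 is affected and k could be near zero.

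Finally, the plan already covers secondary measures with regression and analysis of variance, so mean CGI change in all children is planned. That protects the overall CGI result, but does not repair the individual classification.

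**Conclusion.** The point holds as a fault in a stated rule. The text allows entry at any CGI severity and imposes no starting condition. The floor argument then follows by arithmetic, given 1-to-7 scoring and change read as improvement. Crediting without crossing depends on where the cutoff and RCI are set.

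The documents do not support the stronger conclusion that low-starting children will be counted as failures and bias a reported rate downward by a known amount. No proportion or denominator is stated, the number of such children is unknown, and the two defects act in opposite directions. The range of 88% to 58% shows what a ceiling would look like and is not an estimate.

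Severity is minor. The CGI is a secondary outcome in a single-arm pilot. The listed aims concern plasma level, feasibility and tolerability, and the primary blood glutathione result does not depend on this rule.

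**What to change.** First set the cutoff and the RCI, since the condition cannot be applied without them. Then add to the rule in Data Analysis, in substance:

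> Clinically significant change will be assessed in children whose Visit 1 CGI severity score is at or above the cutoff and exceeds the scale minimum by more than the RCI. The Visit 1 score is also the baseline for change. The proportion among these children, and the number not meeting the condition, will be reported beside the figure for all children in the intention-to-treat population and the planned analysis of mean CGI severity.

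Eligibility and change should use the same score. Deciding eligibility at screening while measuring change from Visit 1 would let both defects return: a child eligible at screening could be at 1 or 2, or below the cutoff, by Visit 1. Keeping the all-children figure avoids departing from the stated population.

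The cost is a few sentences in the plan and no new data. The restricted proportion has a smaller denominator and a wider interval. Selecting on baseline severity in a single-arm study also adds regression to the mean, so the proportion should be read as descriptive. Repeating it in children who also met the condition at screening is an optional sensitivity analysis.

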The study will end once 24 subjects have been recruited and have completed the study visits. At this point, the data analysis will then begin.

Potential Risks and Benefits:

The study supplement Glutathione may help to decrease problem behaviors and irritability that can be seen in children with Autism Spectrum Disorder. It is also postulated that the information learned from this study will benefit other individuals and children and adolescents with problem behaviors related to Autism Spectrum Disorder in the future.

Page 11 of 17 IRB19-0017 Version 2; date: 4/11/19 Most supplements can cause side effects, but are typically safe. Side effects are usually reversible when the supplement is stopped. The most common side effects associated with Glutathione include; upset stomach, diarrhea, dizziness, dry mouth or headaches and sometimes, but rarely a skin rash, skin flushing or respiratory distress can be seen. As such, patients with asthma or allergies that have resulted in respiratory distress in the past will not be included in this study to ensure safety.

Safety Assessments:

Safety assessments (sitting blood pressure, heart rate, adverse effects, and concomitant medications) will be documented at each visit. In terms of vital signs, those subjects with abnormal blood pressures will be assessed for symptoms of hypo- or hypertension. Asymptomatic subjects will be evaluated each visit for changes in vital signs. In the case of hypertensive emergencies (BP greater than 210/120), appropriate referral to the emergency room will be made. In the case of hypotension (BP less than 90/60), participants will be evaluated for symptoms of hypotension and if symptomatic, appropriate interventions will be made. Subjects who endorse suicidal thoughts at any time during the study will be removed from the study and appropriate clinical intervention (e.g. hospitalization) will be arranged.

At the initial visit, blood work will be obtained for a baseline Glutathione level and an end point Glutathione level will also be obtained at study completion. Assessment of side effects will be done at each visit. Participants will be advised concerning the risk of allergic reactions to Glutathione: skin rash, skin flushing, drop in blood pressure, irregular heartbeat, and respiratory distress. Although is it extremely rare but participants will be advised to visit an emergency room for symptoms suggestive of anaphylactoid reactions.

Adverse Event Reporting:

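### Does the numbered exclusion list leave out the allergy exclusion that the risk section promises?

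*Combined protocol and SAP*

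**What the plan says.** The protocol deals with this in two places.

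- **Potential Risks and Benefits.** Among the side effects of the supplement it notes that "sometimes, but rarely a skin rash, skin flushing or respiratory distress can be seen". From this it draws an eligibility consequence: "patients with asthma or allergies that have resulted in respiratory distress in the past will not be included in this study to ensure safety".
- **Exclusion criteria.** The numbered list prints items 1 to 9, then 11 and 12. The asthma half of the precaution is there: "12) Asthma (given this is rare, but possible worsening of asthma symptoms due to Glutathione". The nearest general item is "1) Unstable medical illness or clinically significant abnormalities on physical examination". No printed item mentions allergy, an allergic reaction or earlier respiratory distress.

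Three other places bear on it. Participant Exclusion, a separate paragraph, restates the age limits and nothing else. Under Assessments, before treatment starts, "all subjects will have a psychiatric, medical, and family history evaluation completed as part of their standard clinical care", and a physical examination takes place at screening. Safety Assessments has families told about allergic reactions and about going to an emergency room if symptoms suggest one.

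**The concern.** Screening staff usually work from the numbered criteria. Here those criteria carry only half of a precaution that the protocol justifies on safety grounds. Item 1 would not obviously catch a currently well child, without asthma, whose allergy once caused breathing trouble: the illness is not unstable and the examination may be normal. The list does look back in time for other conditions, for example "3) History of Hematological disorders", so a line on past allergic respiratory distress would have fitted its form, and its absence looks like an oversight.

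At stake is the enrolment of a child whom the risk section says will not take part, in an open-label study of children aged 4 to 17. That would be a safety matter and a departure from the approved protocol. It would not be a statistical matter.

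**Working it through.** No formula applies, and the plan gives no figure to reproduce. The check is a comparison of texts.

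1. **Count of the list.** Printed items: 9 (items 1 to 9) + 2 (items 11 and 12) = 11. Items naming asthma: 1 of 11 (item 12). Items naming allergy or past respiratory distress: 0 of 11. Numbers absent from the sequence: one, item 10.

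2. **Do the two places contradict each other?** A contradiction would need one place to admit a child whom the other refuses. The list states who is excluded; it does not say that children with such allergies are eligible. The risk section adds a group to those excluded. Both can be obeyed at once, and the combined rule keeps out children with asthma and children whose allergies have led to respiratory distress.

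3. **Does the wording on asthma change this?** In the risk section, the qualifier about past respiratory distress could attach to allergies only, or to asthma as well. Item 12 excludes asthma without that qualifier. Under either reading, obeying both places excludes all asthma and the allergy group, so the ambiguity does not affect the outcome.

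4. **Is the list presented as the only source of exclusions?** No. Participant Exclusion also states exclusions outside the list, although on age only. The protocol's opening statement bars departures from the protocol without prior IRB approval, apart from removing an immediate hazard. That covers the whole protocol, including the risk section.

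5. **What can be said of item 10?** Its neighbours both concern concomitant treatment: "9) Current treatment with N-acetylcysteine, milk thistle, Vitamin C, Vitamin B, Grape Seed Extract, Amino Acids, or Zinc (known to interfere with Glutathione level" and "11) Current treatment with Dextromethorphan, D-cycloserine, Amantadine, Memantine, Lamotrigine or Riluzole (known to have glutamatergic properties". That hints that a lost line might also have concerned treatment, but asthma follows at item 12, so it is no more than a hint. The available text does not show whether item 10 was misnumbered or lost in reading the PDF. A line lost that way cannot be counted as missing from the plan.

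6. **Consequence for the analysis.** The document gives no prevalence of such allergies in the clinic population, so the number affected among the 24 planned children cannot be calculated. The primary outcome (change in blood glutathione), the analysis methods and the sample size rationale do not depend on where this exclusion is written.

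**The case for a change.** The best case for acting is that a safety exclusion belongs where screeners look, and that the remedy is one line. The protocol takes the risk seriously enough to give emergency-room advice. The history and examination may uncover a past episode, but no printed item tells the screener that the episode excludes the child. Advice to families about allergic reactions is not an eligibility rule either.

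Much of this stands. The list as printed is less complete than the risk section, and a tidy protocol would state the exclusion in both places. What does not stand is the step from there to a defect in the plan. The route to harm needs a screener who uses the numbered list and ignores the rest of the protocol, and nothing in the document says that screening works that way. Screening forms and consent pages are not available, so what parents are asked is unknown, and that silence cannot be held against the plan. The history evaluation and examination are not eligibility rules, but they make it less likely that an episode goes unnoticed. Adding the line would copy a rule that the protocol already contains; it would create no new protection on paper.

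**Conclusion.** The observation is accurate: 0 of the 11 printed items carry the allergy exclusion, and item 10 is not printed. It is nevertheless a clerical matter. The protocol already says that such children will not be included, the two places can be obeyed together, and a study run as written excludes them. No statistical figure, result or conclusion changes.

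This rests on two assumptions: that the whole protocol governs enrolment, which its opening statement on deviations supports, and that the risk-section sentence means what it says. It does not depend on what item 10 contained. If that item covered such allergies, even the editorial point disappears. If it did not, the list and the risk section differ in completeness but not in substance. It is reasonable to ask the investigator what item 10 was and to align the two wordings at the next convenient revision.
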